2.3 Contraindications

- Patients who have not received antiplatelet agents prior to the procedure.
- Patients with active bacterial infection.
- Patients in whom antiplatelet and/or anticoagulation therapy is contraindicated.
- The Pipeline™ Flex embolization device with Shield Technology™ should not be used alone as sole therapy for acutely ruptured aneurysms.

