 - If the intervention started in the same month and year as the study procedure, the intervention start-date will be assumed to be the date of the study procedure (i.e., Study Day 0);
 - Otherwise, the intervention start-date will be assumed to be the 15th day of the given month and year, e.g., XX-DEC-2015 ▪ 15-DEC-2015 where XX represents an unknown value.
- In the event that the day and month portion (and only the day and month portion) of the intervention start-date are missing:
 - If the intervention started in the same year as the study procedure, the intervention start-date will be assumed the date of the study procedure (i.e., Study Day 0);
 - Otherwise, the intervention start-date will be treated as June 15th of the given year, e.g., XX-XXX-2015 ▪ 15-JUN-2015.
- In the event that the day, month, and year portion of the intervention start-date are missing, the start-date of the intervention will be assumed to be the date of the study procedure (i.e., Study Day 0).

Note: With the exception of following special cases, this conservative scheme ensures that an intervention with a partially or completely missing start-date will be treated as post-procedural.

Special Cases on Missing Intervention Start-dates

- Using the above rules for the handling of missing intervention start-dates, if the assumed intervention start-date:
 - is later than the reported intervention stop-date, the assumed intervention start-date will be reset and assumed to be the intervention stop-date.
- If, based on the above rules, it cannot be determined whether the intervention was taken prior to the study procedure, it will be assumed to be post-procedural.

Investigation of the Effect of Investigational Sites

As an exploratory analysis, the results by site will be examined: Small sites (i.e., sites that have less than 4 subjects) will be identified and the following method will be used for combining the data. Data from all small sites (<4 subjects) will be combined to form a single site in order to obviate non-estimable situations in the evaluation of site and site interaction effects. Once combined, the pooled site will remain as such for all analyses for which a site effect is determined. If the pooled smaller sites represent a single site that has more than twice as many subjects as the largest single site, however less than 3

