The incidence of complete aneurysm occlusion without significant parent artery stenosis ($\leq 50\%$) at 1 year post-procedure and without re-treatment of the target aneurysm (Primary Efficacy Endpoint) will be based on the Scale of Roy. Results will be based on the ITT population and will include the target aneurysm for each patient. The target aneurysm is defined as the largest aneurysm treated in the study procedure as identified by the core laboratory.

Results based on the ITT population will be presented in a table entitled *Overall Summary of the Post-Procedure Variables by Time*. The table will contain the point estimate and the confidence limit based on the exact Clopper-Pearson method. The supportive data for this table will be presented in a listing entitled *Post-Procedure Variables*. This listing will be sorted by patient number. Results based on the ICA population will be presented in a similar table and results based on the FAS population will be presented in a similar table.

Concomitant Medications

Concomitant medications refer to all medications taken from Day 0 thru study exit. *Antiplatelet medications were collected per their actual start date even if these were started prior to the study treatment (Day 0)*. *Prior medications* refer to all medications that were started and stopped prior to the first treatment with the Pipeline™ device with Shield Technology™ and will not be reported as concomitant.

The count and percent of subjects on anti-platelet medications will be summarized for 7 days pre-procedure, as well as for post procedure (were available) and presented in tables entitled *Summary of Dual Antiplatelet Therapy (DAPT)*. A summary of the concomitant medications will be presented in a table entitled *Summary of Concomitant Medications*, containing a clear declaration regarding the start date of the medication relative to the study procedure. The concomitant medications taken by the ITT population will be displayed in a listing entitled *Concomitant Medications*.

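### For antiplatelet drugs continued through the procedure, the Day 0 default for incomplete start dates removes true pre-treatment from the 7-day pre-procedure table

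*SAP*

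**What the plan says.** SAP 7.4, under the heading on missing start dates for interventions, works by which part of the date is absent.

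- Only the day is missing: "If the intervention started in the same month and year as the study procedure", the start is set to Day 0. "Otherwise, the intervention start-date will be assumed to be the 15th day of the given month and year".
- Neither day nor month is known, so the year decides: "If the intervention started in the same year as the study procedure, the intervention start-date will be assumed the date of the study procedure". For a different year the plan gives a fixed date: "Otherwise, the intervention start-date will be treated as June 15th of the given year".
- The whole date is missing: the start is set to Day 0.
- If the imputed start falls after a recorded stop date, it is moved back to the stop date.
- Where, after all this, "it cannot be determined whether the intervention was taken prior to the study procedure, it will be assumed to be post-procedural".

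A Note between the rules and the special cases calls the scheme conservative. It says that, apart from the special cases, every partial or missing start will be handled as post-procedural.

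SAP 7.7, under Concomitant Medications, then plans the antiplatelet table: "The count and percent of subjects on anti-platelet medications will be summarized for 7 days pre-procedure". It makes no exception for imputed dates. The same section says that antiplatelet drugs were recorded by their real start date even when that preceded Day 0.

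Protocol 2.3 lists among the contraindications: "Patients who have not received antiplatelet agents prior to the procedure". Exclusion criterion 6 excludes anyone with a known contraindication to the device. Protocol Table 5-1 has a baseline item on antiplatelet use in the previous 30 days.

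**The concern.** SAP 7.4 does not define an intervention. It does speak of interventions being taken and having stop dates, which fits medication, and the visible SAP has no other rule for medication dates. Antiplatelet drugs therefore come under it.

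For most drugs, treating an uncertain start as post-procedural is a tolerable convention. For antiplatelets the direction is unfavourable. The eligibility criteria imply that each eligible subject had at least one such agent beforehand, and this is the class whose pre-procedure starts the study deliberately records. An ongoing drug dated Day 0 drops out of a window that ends at the procedure.

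At stake are the antiplatelet table and the concomitant-medication table, which must state start dates relative to the procedure. Protocol 1.3 gives the description of DAPT regimens, and their association with thrombotic and haemorrhagic events, as an aim of the study. Pre-procedure exposure therefore matters even though it is only described.

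**Working it through.** The plan states no figure on this point, so there is none to reproduce. The check applies the SAP 7.4 rules to known true start dates and counts how many pre-procedure starts end up on Day 0.

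**Assumptions.** Procedure dates are spread evenly over the calendar (730 dates in two 365-day years). The drug is still being taken at the procedure, so the stop-date rule does not act. The 7-day window ends before Day 0. The true start is k days before the procedure.

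**Only the day missing.** The start moves to Day 0 when it lies in the procedure month. A month of length L has L − k procedure dates for which this is so. Summed over 12 months, the share is (365 − 12k)/365 for k up to 28. At k = 30 only the seven 31-day months contribute, one date each.

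**Day and month missing.** The start moves to Day 0 when it lies in the procedure year: (365 − k)/365.

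**Whole date missing.** It always moves to Day 0.

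| True start, days before | Day missing | Day and month missing | All missing |
|---|---|---|---|
| 5 | 305/365 = 83.6% | 98.6% | 100% |
| 7 | 281/365 = 77.0% | 98.1% | 100% |
| 14 | 197/365 = 54.0% | 96.2% | 100% |
| 21 | 113/365 = 31.0% | 94.2% | 100% |
| 30 | 7/365 = 1.9% | 91.8% | 100% |
| 90 | 0% | 75.3% | 100% |
| 180 | 0% | 50.7% | 100% |

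**Examples, procedure on 20 March 2017.**
- March 2017, day unknown: 20 March, so Day 0.
- March 2017, day unknown, stopped 18 March: 18 March, before the procedure.
- February 2017, day unknown: 15 February, before the procedure.
- 2017 only: 20 March, so Day 0.
- 2016 only: 15 June 2016, before the procedure.

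The February and 2016 examples contradict the Note. They are partial dates, neither is a special case, and both are placed before the procedure.

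**From records to subjects.** A subject appears untreated only if every antiplatelet record moves to Day 0. If just one of two drugs moves, the subject appears to be on a single agent.

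The frequency of incomplete dates is not in the documents, so the share f below is an assumption. Take 200 subjects, all truly pre-treated. In a share f, every antiplatelet start lacks only the day, the true start is 7 days before, and the subject's drugs began together. Subjects shown as untreated = 200 × f × 0.770; reported use = 1 − 0.770f.

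| f | Shown untreated | Reported use | If those dates are fully missing |
|---|---|---|---|
| 5% | 7.7 | 96.2% | 10 subjects, 95% |
| 10% | 15.4 | 92.3% | 20 subjects, 90% |
| 20% | 30.8 | 84.6% | 40 subjects, 80% |

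The true value in every row is 100%.

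**The case against.** The best defence is that the rule reaches less far than its Note suggests. An earlier month or year is imputed before the procedure, and a pre-procedure stop date pulls the start back. With only the day missing, the error has almost gone by 30 days, and SAP section 5 allows for starts more than 30 days before the procedure. One usable date on either DAPT drug keeps the subject in the count. All of this stands and limits the point to the three Day 0 cases.

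A reader might infer that Day 0 is wrong for nearly every antiplatelet record. The contraindication does not support that. It calls for some antiplatelet agent beforehand, not for every recorded drug to predate the procedure. SAP 7.7 and 7.13.3 allow for therapy changes after platelet testing, so a replacement drug begun afterwards is correctly post-procedural.

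A reader might also expect false protocol deviations. SAP 7.4 takes deviations from case report form entries and tabulates them by code, and nothing derives them from imputed dates.

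The plan has safeguards. Sites are queried about omissions (Protocol 13.1), antiplatelets are recorded by real start date, and imputed values are flagged in listings and kept out of raw data (SAP 7.2.1). These reduce the number of incomplete dates or make them visible. They do not change how an unresolved date enters a table built on derived data. SAP 7.4 also lets unresolved missing data be left out of tabulations, but only at discretion, and it does not say when that overrides the date rules.

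Finally, the baseline 30-day item might feed the 7-day table. The visible SAP does not say so, and 30 days of history does not settle 7-day status.

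**Conclusion.** The point holds in limited form. For an antiplatelet drug continued through the procedure, an incomplete start date that meets one of the three Day 0 conditions is probably misclassified, in the direction that the eligibility criteria make unlikely. For a start one week before, this affects 77% of records lacking only the day and 98% of those lacking day and month. It affects every fully missing date, whenever the drug began.

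The effect on the table depends on the unknown frequency of such dates. Across the assumed 5% to 20% of subjects with all antiplatelet starts lacking only the day, reported use would fall from 100% to between about 96% and 85%. These figures also rest on an even spread of procedure dates and on the SAP's table using imputed starts.

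The damage is confined to descriptive exposure tables. It would be tempting to conclude that the DAPT-to-event association is biased, but the visible SAP specifies no such model, and some of its additional safety analyses are redacted. No primary or secondary endpoint uses these dates. The matter is worth settling before analysis, but it does not threaten the main results.

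**What to change.** Amend SAP 7.4 and 7.7 as follows.

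1. Exempt antiplatelet agents from the Day 0 default.
2. Classify an antiplatelet record with an incomplete start as pre-procedure only where drug-level baseline or pre-procedure medication data support it. The past-30-days item can serve, together with the stop date or ongoing status. A subject-level yes on that item should not backdate every drug the subject took.
3. Show all other such records as timing unknown in the 7-day table. Add a sensitivity count with the unknowns taken first as pre-procedure and then as not.
4. Reconcile the Note in SAP 7.4 with the 15th-of-month and 15-June rules, so that a programmer following either gets the same date.
5. State whether the baseline item feeds the 7-day table. If it already does, saying so would close much of the point.

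The cost is SAP wording, minor programming and a small unknown category in the table. The protocol already plans the baseline item, so no new data collection is needed.

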The PUFs study was a multicenter, prospective, single-arm trial to evaluate the safety and effectiveness of the PED in complex large and giant IAs.²⁸ One hundred seven subjects with large and giant unruptured wide-necked aneurysms in the petrous to the superior hypophyseal segment of the ICA were treated with the PED. The aneurysms measured ≥ 10 mm in diameter and had either a neck ≥ 4 mm or no discernable neck. A total of 104 subjects with 106 aneurysms were included in the primary effectiveness cohort. Of the 106 aneurysms, 78 demonstrated complete occlusion without major stenosis at 180 days (73.6%; 95% posterior probability interval: 64.4%–81.0%). At one year, 86.8% (79/91) of the target aneurysms were completely occluded. This rate increased to 95.2% (59/62) complete occlusion at five years. There were no cases of aneurysm recurrence. The primary safety endpoint was the occurrence of major ipsilateral stroke or neurologic death at 180 days, which occurred in six of the 107 subjects (5.6%; 95% posterior probability interval: 2.6%–11.7%). At five year follow-up, the rate of major ipsilateral stroke or neurologic death remained 5.6%.

International Retrospective Study of the Pipeline Embolization Device (IntrePED)

The IntrePED study was a retrospective global post market study of subjects treated with the PED at 17 centers worldwide.²⁹ A total of 793 subjects with 906 aneurysms of various sizes and locations were included. The median follow-up period was 19.3 months with 89% subjects with greater than 1 year follow-up. The overall neurological morbidity rate was 7.4% (59/793) and the neurological mortality rate was 3.8% (30/793). The combined neurological morbidity and mortality rate was 8.4% (67/793). The combined neurological morbidity and mortality for treated ruptured aneurysms was higher at 18.4% (14/76). Data from the IntrePED study report the safety of the PED in the treatment of various IAs in a real-world clinical setting.

Aneurysm Study of Pipeline in an Observational Registry (ASPIRe)

ASPIRe was a prospective, multi-center, single arm, post-market registry of 191 IA patients with 207 aneurysms from 28 worldwide centers who underwent PED treatment. The 207 aneurysms in the study had a median follow-up duration of 6.6 months. The majority of aneurysms treated were saccular and overall average size of treated aneurysms was 14.5mm.

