The non-ICA is a subset of the ITT population including only those subjects in whom the Pipeline™ device with Shield Technology™ was implanted in the arterial vessels other than those specified in the ICA population.

6. Determination of Sample Size

No formal estimates were prepared for examining the individual variables. However, the incidence of certain events will be examined relative to the thresholds used in research treating a similar population. Device outcomes variables recorded on a dichotomous scale will be summarized using a 2-sided 95% Clopper-Pearson exact binomial confidence interval. The upper and lower bounds of the confidence interval will be examined relative to results in the peer-reviewed literature and studies using the

Pipeline device without the Shield Technology™. Specifically, the incidence at 1 year post-procedure of a major stroke in the territory supplied by the treated artery or neurological death will be examined relative to an a priori threshold of 15%. The incidence at 1 year post-procedure of aneurysm occlusion without significant parent artery stenosis will be examined relative to an a priori threshold of 50%.

7. Statistical Methods

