7.2.2 General Conventions for Summarization

Summary statistics will consist of the number and percentage of responses or counts at each level for categorical variables (e.g. gender). For continuous variables, the sample size (n), mean, median, standard deviation (SD), minimum, and maximum values will be presented.

All mean and median values will be formatted to one more decimal place than the measured value. Standard deviation values will be formatted to two more decimal places than the measured value. Minimum and maximum values will be presented with the same number of decimal places as the measured value.

The number and percentage of responses will be presented in the form XX (XX.X%).

- All summary tables will include the analysis population sample size (i.e., number of subjects).
- Relative Study Day 0 is defined as the day the patient underwent the study procedure. All study days are determined relative to the day the patient underwent the study procedure.
- Baseline values will be defined as those values recorded immediately prior to the study procedure.
- Change from baseline for differences will be calculated as follows:

$$\text{Change} = \text{Post-baseline value} - \text{baseline value}$$

- Missing data may have an impact upon the interpretation of the trial data. The primary presentation of the overall primary endpoint results will be based on the observed data with multiple imputation for missing data using SAS PROC MI. A methodology is also defined in this section for addressing missing dates.
- Date variables will be formatted as DDMMYYYY for presentation; SAS Date9. format.

Data from this study, when applicable will be presented in a listing format. All listings will be sorted by patient number and date, as applicable.

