times as many subjects, the small sites will be ranked by size and divided into 2 pooled assignments using an alternating sequence (ABABAB). If the pooled smaller sites represent a site that has more than three times as many subjects as the largest single site, however less than 4 times as many subjects, the small sites will be ranked by size and divided into 3 pooled assignments using an alternating sequence (ABCABCABC).

Imputation of Outcome Data

Missing data for subjects who fail to complete study follow-up without any evidence of a major stroke in the territory supplied by the treated artery or neurological death will be imputed in the analysis of primary safety using the multiple imputation procedure from SAS (Proc MI). Subjects who withdraw from the study prior to completion and have experienced a major stroke in the territory supplied by the treated artery or neurological death at any time will be counted as having experienced the event of interest. A separate tabulation will be provided based on the observed data: subjects who withdraw from the study prior to completion without any evidence of a major stroke in the territory supplied by the treated artery or neurological death will be counted as not having experienced the event of interest. For effectiveness, since follow-up imaging of the target aneurysm was not required at each study visit but was instead performed according to standard of care, the primary endpoint will be assessed using a selection rule, according to the following preferences:

- Imaging from day 141 (the opening of the 6-month follow-up window) onward is eligible to be included; imaging earlier than day 141 is disregarded for this analysis but imaging after the end of the 1 year window is still eligible.
- We will use the last adjudicated image at any time starting from day 141, UNLESS
- - o The last image is a CTA and there is a DSA within 90 days prior to the CTA, in which case the DSA will be used, OR
 - o The last image is an MRA and there is a DSA or CTA within 90 days prior to the MRA, in which case the DSA or CTA will be used. For this sub-rule we will prefer DSA over CTA if both exist.

The rules above define the available data for the purpose of endpoint calculations and effectiveness tables and listings. For subjects with no qualifying imaging per the above preference rules, multiple imputation will be employed to handle missing data for primary effectiveness.

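### Primary safety: only event-free non-completers go to PROC MI, with no model, use of event-free time or pooling rule stated; run as a single binary 1-year indicator, this biases the rate upward, and the interval can under-cover once non-completion reaches roughly 20%.

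*SAP*

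**What the plan says.** The rule is in SAP 7.4, under Imputation of Outcome Data. It covers "Missing data for subjects who fail to complete study follow-up without any evidence of a major stroke" in the treated territory "or neurological death will be imputed in the analysis of primary safety using the multiple imputation procedure from SAS (Proc MI"). Subjects who withdraw early but "have experienced a major stroke in the territory supplied by the treated artery or neurological death at any time will be counted as having experienced" that outcome, so their events stay in the data as observed.

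SAP 7.2.2 gives the imputed result its status: "The primary presentation of the overall primary endpoint results will be based on the observed data with multiple imputation for missing data". An un-imputed version is also planned: "A separate tabulation will be provided based on the observed data: subjects who withdraw from the study prior to completion without any evidence" of an event are counted there as event-free.

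For the interval, SAP 6 says: "Device outcomes variables recorded on a dichotomous scale will be summarized using a 2-sided 95% Clopper-Pearson exact binomial confidence interval". The same section states that the 1-year safety incidence "will be examined relative to an a priori threshold of 15" percent.

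The readable text gives no imputation model, covariates, number of imputations or combining rule. It does not say whether time already spent event-free enters the imputation, although SAP 7.2.1 derives duration on study for every subject. SAP 7.9 lists worst-case and tipping-point analyses for effectiveness only. The additional safety list in SAP 5 is redacted and may contain one for safety.

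**The concern.** SAP 6 treats the endpoint as a dichotomous 1-year incidence, so an analyst following 7.4 would most naturally give PROC MI one yes/no variable. Whether that variable is missing then depends on its value, because a dropout's status is known only if it is an event. Events among dropouts stay in the set that informs the imputation, while event-free dropouts leave it. Each event-free dropout is then assigned a full year's risk again, including months already passed without an event.

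The protocol's own background shows why elapsed time matters. In an earlier single-arm trial, the endpoint was "major ipsilateral stroke or neurologic death at 180 days, which occurred in six of the 107 subjects" (5.6%), and the rate was still 5.6% at five years. No events after day 180 are therefore reported, although that trial enrolled only large and giant unruptured carotid aneurysms and later losses may hide events. On that pattern, a subject who leaves at month 8 has little risk left.

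At stake is the primary safety rate, which is to be set against 15%, contrasted with earlier Pipeline studies and used for a US indication evaluation (SAP 3 and 6). Some non-completion is built in: implant failures belong to the ITT population but are followed only to discharge (SAP 5; Protocol 6).

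**Working it through.** The plan states no sample-size calculation, event rate or dropout rate for this study, so there is no figure of its own to reproduce.

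**Inputs**
- N = 200, the planned maximum (Protocol 4.2).
- True 1-year rate p = 6.8%. This is a proxy: 13/191 in the prospective registry of Protocol 1.2.3, for a broader endpoint.
- Dropout d = 2, 5, 11, 20 and 30%: assumptions. The only anchor near 11% is the retrospective study in Protocol 1.2.3, where 89% had more than one year of follow-up.
- Share s of dropouts' events seen before exit: 12/13 if events are mostly early, 1/2 if events and dropout are both spread evenly over the year. The 12/13 is a proxy that combines two registry counts: 12/191 with major adverse events within 30 days, and 13/191 with morbidity or mortality overall.
- Dropout is non-informative.

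**Formula**
- Observed events per subject: p(1 − d + ds). This is also the expected un-imputed rate.
- Share with known status: (1 − d) + dps.
- An intercept-only binary imputation fills the remainder at the rate seen among those with known status, so the overall rate is MI = p(1 − d + ds) / [(1 − d) + dps].
- Bias = MI − p = p(1 − p)ds / [(1 − d) + dps]. It is zero if s = 0 and positive otherwise.

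Example, d = 0.11 and s = 12/13: numerator 0.068 × (0.89 + 0.1015) = 0.0674; denominator 0.89 + 0.0069 = 0.8969; MI = 7.52%, a shift of +0.72 points.

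| Dropout | MI, s = 12/13 | MI, s = 1/2 | Un-imputed, s = 12/13 | Un-imputed, s = 1/2 |
|---|---|---|---|---|
| 2% | 6.92% | 6.87% | 6.79% | 6.73% |
| 5% | 7.11% | 6.97% | 6.77% | 6.63% |
| 11% | 7.52% | 7.19% | 6.74% | 6.43% |
| 20% | 8.24% | 7.59% | 6.70% | 6.12% |
| 30% | 9.24% | 8.14% | 6.64% | 5.78% |

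Simulation (N = 200, dropout uniform over the year) agrees. With mostly early events it gives 6.9, 7.1, 7.5, 8.3 and 9.3%; with evenly spread events, 7.0, 7.2, 7.7 and 8.2% at 5, 11, 20 and 30%. For the 180-day pattern above (p = 6/107, s = 0.753), the formula gives 6.1% at 11% dropout and 6.6% at 20%.

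**Coverage of a nominal 95% interval** (simulated, 6.8%, mostly early events). SAP 6 names Clopper-Pearson but does not say how to apply it to imputed data, so four versions were tried.

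| Dropout | Clopper-Pearson, averaged count, n = 200 | Clopper-Pearson, effective n | Rubin, Wald | Rubin, logit |
|---|---|---|---|---|
| 5% | 95.1 | about 96 | 94.8 | about 94 |
| 10-11% | 93.3 | about 95 | 94.6 | about 93 |
| 20% | 85.9 | about 91 | 92.8 | about 87 |
| 30% | 72.8 | about 82 | 87.5 | about 77 |

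**Against 15%.** The chance that the upper limit falls below 15% (averaged-count Clopper-Pearson versus Kaplan-Meier with a log-log interval) is 89% versus 95% at 11% dropout, and 78% versus 95% at 20%. Clopper-Pearson upper limits evaluated at the expected MI rate with s = 12/13 are 12.95% (n = 200) or 13.58% (effective n 163) at 20% dropout, and 14.13% or 15.21% (effective n 144) at 30%. With no dropout the limit is 11.2%.

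**Using event-free time.** The Kaplan-Meier 1-year risk averages 6.8% at every dropout level from 2% to 50%, with 95.2-95.5% coverage. Imputation by visit interval gives 6.81, 6.85, 6.91 and 6.96% at 5, 10, 20 and 30% dropout, with coverage of about 95%.

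**The case against.** The strongest reply is that this is underspecification, not a demonstrated error. The SAP does not say that one binary indicator will be used, and its counting rule does not force one; imputation conditional on event-free time would be unbiased under the same rule. That stands, and the conclusion is conditional for this reason. A reader might infer that the SAP mandates a biased estimate. It does not: it leaves room for one and makes it the easiest implementation.

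A reader might also infer that the interval under-covers generally. The coverage table does not support that. At 5% dropout every method is close to 95%, and at 10-11% the loss is slight.

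High dropout may be unlikely. Protocol 5.5 plans contacts through month 12 with an 8-week window, and Protocol 5.9.3 requires three attempts, the last by registered letter. The only illustration of missing data in SAP 7.9 (98/196 with 200 in ITT) corresponds to 2%, though it is an example and not a forecast. At 2% the bias is about 0.1 point, and at 11% it is about one subject in 200 (0.4 to 0.7 points × 200 = 0.8 to 1.4).

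The error is conservative for the device, Protocol 9.2 sets no success criterion, and the un-imputed tabulation will appear beside the imputed rate. All of this stands and limits the severity. It does not remove the point, because the imputed figure is the primary one and its interval is undefined.

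Finally, a reader might infer that non-neurological deaths will be assigned imputed strokes. The SAP imputes missing data, and a death adjudicated as non-neurological need not be treated as missing. The text is silent, so a sentence is worth adding.

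**Conclusion.** The concern holds in conditional form. If 7.4 is implemented as one binary 1-year indicator, dropout is non-informative and some dropouts' events are seen before exit, the primary safety rate is biased upward. The shift is small at low dropout and reaches +0.8 to +1.5 points at 20% for a true 6.8%. Under-coverage is a problem from roughly 20% non-completion, and its size depends on an interval method that the SAP does not define.

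These figures rest on assumed dropout rates and on event timing borrowed from an earlier registry, whose median follow-up of 6.6 months may itself hide late events. There is no bias if none of the dropouts' events can be seen, and the direction reverses if their later risk exceeds the imputed rate. The documents do not support a claim that the study would wrongly miss its 15% threshold: the threshold is only a reference, and an expected upper limit above 15% appears only at 30% dropout with mostly early events, and only under some interval methods.

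The point is worth fixing before database lock, because two analysts following the present text could report different primary rates and intervals.

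**What to change.** Amend SAP 7.4 in one of two ways.

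1. Keep multiple imputation as primary, and state that event-free non-completers are imputed only the risk remaining after their last contact. One version imputes by visit interval to days 30, 90, 180 and 365, merging any interval without events with its neighbour. State the model and the number of imputations. Pool by Rubin's rules on the logit scale, in place of Clopper-Pearson on completed data.
2. Or make the Kaplan-Meier 1-year risk with a log-log interval the primary estimate (Aalen-Johansen if non-neurological deaths are treated as competing events). This is simpler and avoids the question of empty intervals.

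In either case, keep the un-imputed tabulation and state that subjects who die of non-neurological causes receive no imputed later event.

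The cost is a short SAP amendment and a little programming; the procedure, event and last-observation dates already exist. The downsides are that the interval is no longer exact binomial and that non-informative dropout is still assumed. The visit-interval version also keeps a small upward bias: at most about 0.2 points when events are early or all fall by day 180, and about 0.5 points at 30% dropout with evenly spread events (7.28% against 6.78%).
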